**April 14, 2018**

# **Efficacy Study of Yi-Zhi-An-Shen Granules for Older Adults with Amnestic Mild Cognitive Impairment**

## **Study Protocol with SAP**

### **1. Objectives**

The primary objective of this study is to evaluate the efficacy and safety of Yi-Zhi-An-Shen Granules (YZASG) in optimizing cognitive performance over time in elderly individuals with amnestic mild cognitive impairment (aMCI). Secondly, the investigators intend to assess whether YZASG can improve sleep quality among aMCI patients. Finally, participants' fecal genomic DNA will be extracted to analyze the gut microbial differences between individuals with aMCI and ones with normal cognition.

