### **3.3.3 Other outcomes**

To assess the safety of YZASG compared to placebo in subjects with aMCI, the investigators will record the incidence and severity of treatment-emergent adverse events (TEAEs), and clinically important changes in safety assessment results (including vital signs, weight, clinical laboratory tests, physical and neurological exams, ECGs, and MRIs).

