### **4.2 Statistic analysis**

Analysis will be conducted by a statistician of the National Clinical Trial Center of Chinese Medicine (Chengdu, China), who will be blinded to the whole trial and using SAS 9.2 software (Cary, NC, USA) and SPSS 19.0 software (IBM, NY, USA).

Unless otherwise specified, all mechanism, efficacy and safety analyses will be strictly conducted according to the intention-to-treat (ITT) principle and the full analysis set (FAS) population, the per-protocol set (PPS) population and the safety set (SS) population. Missing values will be replaced by the last observation carried forward (LOCF) method. ADAS-cog (including its monomial item) changes from baseline and the secondary outcomes will be assessed using an analysis of covariance with treatment groups as factors and baseline values as covariates. Standardized mean

differences will be used to express effect sizes in SD. The baseline homogeneity of the baseline characteristics between the two groups will be analyzed with Fisher's exact test, or  $\chi^2$  test for categorical measures and with the *t* test or Wilcoxon rank-sum test for continuous measures. The statistical significance is defined as a one-sided P-value of <0.05 and 95% confidence interval.

For the gut microbiome analysis, sequenced data will be interpreted using the bioinformatics tools programmed in the Ion Reporter software. QIIME algorithms will determine the bacterial diversity within a sample ( $\alpha$  diversity) and among all the samples ( $\beta$  diversity). Additionally, multivariate data analysis with principal component analysis on the diversity indexes and comparisons of genus and species level data will be performed to reveal differences in the microbial composition between individuals with normal cognition and ones with aMCI. The Benjamini–Hochberg false discovery rate adjustment will be used to account for the number of taxa tested in each comparison.

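### The only significance rule in section 4.2 is one-sided and not limited to the directional efficacy hypothesis, so it does not fit the aMCI-versus-normal microbiome comparison, where differences may go either way.

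*Combined protocol and SAP*

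**What the plan says.** Section 4.2 defines significance once: "The statistical significance is defined as a one-sided P-value of <0.05 and 95% confidence interval". The definition closes the paragraph on the analysis of covariance, effect sizes and baseline tests. The sentence just before it concerns baseline homogeneity, which has no direction, so its position does not tie the definition to efficacy.

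The gut microbiome paragraph comes next. Its comparisons are meant "to reveal differences in the microbial composition between individuals with normal cognition and ones with aMCI". On multiplicity it says: "The Benjamini–Hochberg false discovery rate adjustment will be used to account for the number of taxa tested in each comparison". It names no taxon-level test, no sidedness and no FDR level.

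The comparison is a stated aim. Section 1 says that fecal DNA will be used "to analyze the gut microbial differences between individuals with aMCI and ones with normal cognition", and section 3.3.2 lists the gut microbiome among the secondary measures. The only specific directional hypothesis is the ADAS-cog one in section 3.3.1.

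**The concern.** A one-sided test needs a direction chosen before the data are seen. The plan gives one for ADAS-cog and none for any taxon or diversity index. An analyst who follows 4.2 as written must either let the data choose the direction taxon by taxon, or impose one direction on all of them. The first choice raises the error rate above its label; the second cannot see part of what the objective asks about. An analyst who sets the rule aside for the microbiome must choose sidedness and FDR level without guidance, possibly after seeing the results. What is at stake is the list of differential taxa reported for the third objective.

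**Working it through.** **Inputs from the documents.** One-sided 0.05 and Benjamini-Hochberg (BH) over taxa (4.2); 80 participants with aMCI (3.1); 15 to 20 with normal cognition (3.3.2). The plan states no FDR level, power or sample size for this comparison, so it has no figure of its own to reproduce.

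**Assumptions.** FDR level q = 0.05. For the simulation: 100 taxa, independent normal test statistics, 0% or 20% of taxa truly different, standardised difference d = 0.8 or 1.2, 10,000 runs.

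**Step 1: a single test, such as alpha diversity.** The critical value is 1.645 for one-sided 0.05 and 1.960 for two-sided 0.05. If the side is chosen from the data, the type I error at 1.645 is 2 × 0.05 = 0.10.

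**Step 2: BH with the direction taken from the data.** For a symmetric statistic, the one-sided P in the observed direction is p1 = p2/2, where p2 is the two-sided P. BH finds the largest k with p1(k) ≤ kq/m, where m is the number of taxa. Substituting gives p2(k) ≤ k(2q)/m, which is BH at 2q on two-sided P-values. With q = 0.05 this is 0.10. The doubling holds for any q.

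With independent tests, the expected FDR is the null proportion times the effective level:
- No true differences: 1 × 0.10 = 0.10, against 1 × 0.05 = 0.05. Simulated: 0.102 to 0.103, against 0.050 to 0.052.
- 20% true differences: 0.8 × 0.10 = 0.08, against 0.8 × 0.05 = 0.04. Simulated: 0.079 to 0.082, against 0.039 to 0.041.

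**Step 3: BH with one fixed direction for all taxa.** The FDR stays near its label (0.049 to 0.051 with no true differences, 0.038 to 0.041 with 20%). Detection of taxa that differ in the untested direction was 0.000 in every scenario.

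Results with 20% true differences, split evenly between directions (an assumption). Each cell gives the FDR, then the share of all true differences found:

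| Controls | d | Two-sided | Observed direction | One fixed direction |
|---|---|---|---|---|
| 15 | 0.8 | 0.040; 0.532 | 0.080; 0.655 | 0.040; 0.269 |
| 15 | 1.2 | 0.040; 0.954 | 0.080; 0.975 | 0.040; 0.478 |
| 20 | 0.8 | 0.039; 0.700 | 0.080; 0.795 | 0.041; 0.350 |
| 20 | 1.2 | 0.040; 0.987 | 0.081; 0.994 | 0.040; 0.494 |

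The last column depends on the split. With 15 controls and d = 0.8, the share found under one fixed direction is 0.489 if 80% of the true differences lie in the tested direction and 0.084 if 20% do. Two-sided testing finds about 0.53 in both cases.

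**The case against.** The strongest reply is that the microbiome analysis has its own paragraph and its own error control, so the one-sided sentence may never have been meant for it. Two-sided taxon tests with an FDR cut-off are an open reading, and neither harm then occurs. This stands in part: applying the one-sided rule to the taxa is the natural reading of an unrestricted definition, but the text does not say so outright. The reply does not remove the point. The general criterion is written without limit, and the microbiome paragraph supplies nothing in its place.

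Several stronger readings are tempting, and the documents do not support them:
- A reader might infer that half of the real differences would be lost. That needs true differences split evenly between directions and one fixed direction for all taxa; the plan gives neither.
- A reader might infer that the plan promises a 5% FDR and fails to deliver it. No FDR level is stated, so the doubling is relative to whatever level is intended.
- A reader might infer that an excess of adverse events on YZASG could not be detected. Section 3.3.3 provides for recording TEAEs and names no test or direction. The sentence in 4.2 that mentions safety, "Unless otherwise specified, all mechanism, efficacy and safety analyses will be strictly conducted according to the intention-to-treat (ITT) principle", concerns analysis principle and populations, not sidedness.
- A reader might extend the point to beta diversity and principal component analysis. As described in 4.2, these have no sides.

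It is also fair to say that a fully two-sided general rule would settle this point together with the separate mismatch between a one-sided 5% test and a 95% interval. If a one-sided efficacy test is kept, this point remains even after the interval is made consistent.

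**Conclusion.** The point holds as a mismatch between a stated rule and a stated objective. The only significance criterion is one-sided and unrestricted, while the aMCI-versus-normal comparison has no direction. If the rule is applied to the genus, species and alpha-diversity tests, P-values taken in the observed direction double the error rate relative to the intended level, and one fixed direction misses every difference on the other side.

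The factor of two needs only a symmetric test statistic. The simulated FDRs also rest on the assumed q of 5% and on independence, and the detection shares on the assumed number of taxa and effect sizes, so they are illustrations and not predictions for this study.

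The primary ADAS-cog test and the sample size are not affected. The correction is worth making because it concerns a stated objective and costs little.

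**What to change.** Add to section 4.2:
- The one-sided criterion applies only to the directional efficacy hypothesis.
- Taxon-level and two-group alpha-diversity comparisons use two-sided P-values, as does any between-arm safety test or baseline test that is performed.
- Benjamini-Hochberg is applied to the two-sided P-values at a stated FDR level, such as 5%.

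No sidedness needs to be stated for beta diversity or principal component analysis.

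The cost is a sentence or two in the SAP. The downside is that somewhat fewer taxa will be declared different than with one-sided P-values in the observed direction. In the table under the check, the share of true differences found falls from 0.655 to 0.532 (15 controls) or from 0.795 to 0.700 (20 controls) at d = 0.8, and by at most 0.021 at d = 1.2 (0.975 to 0.954).
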